Effectiveness of a Smoking Cessation Algorithm Integrated into HIV Primary Care

Study Protocol

NCT Number: NCT03670316

Date: September 10, 2025

Purpose and Background

Aim 1: Compare the efficacy of Algorithm Treatment (AT) to Enhanced Treatment as Usual (eTAU) control group for smoking cessation among PLWH smokers engaged in HIV clinical care. We hypothesize that the AT group will have a significantly higher proportion of abstinence (biochemically confirmed primary outcome), 24-hour quit attempts, and greater reduction in mean number of cigarettes smoked per day at 6-months post randomization compared to those in the eTAU group.

Aim 2: Characterize provider-, staff-, patient-, and clinic-level facilitators and barriers to integration of AT treatment and examine intervention cost effectiveness in care. We hypothesize that, compared to the eTAU, written pharmacological prescriptions for smoking cessation and provider knowledge and confidence to treat nicotine dependence will be significantly greater in the AT group. We will also describe clinic characteristics such as size, staffing patterns (e.g., number and type of staff, providers, etc.), average number of annual visits by patients, amount of Ryan White funding, and average appointment time to help inform a future wide-scale implementation project across all CNICS sites.

Aim 3: Estimate the cost effectiveness of the intervention relative to the primary smoking outcomes. This will be done by examining the incremental cost per quit of AT vs. eTAU at 3- and 6-months post intervention.

Site and Staff

The University of Alabama at Birmingham (UAB)

[name], Psy.D., Principal Investigator

[name], Co-Investigator

[name], Program Director
[name], Study Coordinator

The University of Washington (UW)

[name] Co-Investigator
[name], Study Coordinator

The Fenway Institute

[name], Co-Investigator
[name], Project Manager
[name], Study Coordinator

Eligibility Criteria & Approach

Eligibility:

CNICS PRO platform will indicate if the patient is eligible or not for the Algorithm study based on smoking scores.

Inclusion criteria:

1. Age 18 or older
2. Receiving HIV care at UAB, UW or Fenway
3. Smoking 5 or more cigarettes per day for the past month. Black and Milds and other cigars don’t count.

Exclusion criteria:

1. Cognitive impairment such that unable to provide informed consent.
2. Non-English speaking
3. Acutely suicidal or intoxicated, manic, or otherwise not stable enough to provide informed consent.
4. Currently receiving smoking cessation treatment

Recruitment Screening and Selection

Participants in the clinic will be identified as eligible through the CNICS PROs (Patient Report Outcomes). Patients enrolled in CNICS complete the PROs at clinic visits roughly 4-6 months apart (90 day minimum). Patients use touch-screen PCs with an easy to navigate interface connected to a network. The following is assessed:

1. **Smoking:**

- a. The Smoking questions are asked at each visit in which a patient completes the PRO.

Pre Screening

UAB

Research staff will utilize a biweekly data query to identify patients who have previously completed a PRO and qualify based on their smoking score. RA/SC will also review the clinic provider schedule every morning to identify any new patients who haven't completed a PRO.

Screening

Patients taking the PRO on the day of the Primary Care Provider (PCP) visit will be screened for the Algorithm study on the CNICS PRO platform based on the inclusion criteria mentioned above. The CNICS PRO will indicate if the patient is eligible/ineligible for the study.

To check for eligibility: The patient must smoke 5 or more cigarettes daily to be eligible for the study and the suicide risk or IPV page was not initiated.

Pages

The Smoking section will trigger two pages/emails to study staff (page initiated through the University of Washington data system).

1. **Page and Email-** Sent at the completion of the Smoking section. Includes: patient's ticket number (ticket generated through CNICS, valid only 48 hours), and day/time.

Approach:

Before entering the exam room listen at the door to be sure that the physician is not present and be mindful not to interrupt clinic staff who may be seeing the patient. Once you have confirmed the patient is alone, greet the patient and approach about the study:

If participant responds 'No', notify main study coordinator and note one of the refusal or postponement reasons below. If a postponement, mark the patient's next PRO date in the tracking log to reapproach then.

Patients who refuse to participate will be informed that this is not a requirement for their care and that their relationship with the clinic will not be affected in any way. If the patient gives a postponement reason, ask the patient "may we contact you again?". If you receive a definite "NO", communicate this to the main study coordinator so study staff will not approach this patient in the future and track the refusal in CNICS. They will note this for entry at the end of the day in the tracking database.

Enrollment

Target Enrollment:

UAB: 250

UW: 200

Fenway: 150

Total: 600

Informed Consent:

For eligible patients, informed consent will be obtained prior to participation in any study-related procedures. Only trained study personnel with appropriate Human Subjects training will detail the requirements of the consent form and study participation with potential enrollees. Study staff will ensure that the participant understands that their consent is voluntary to avoid coercion. Patients will be approached in private rooms or designated study space for informed consent procedures by trained study staff.

When the research coordinator/study staff approaches the patient, they will let him/her know that it is important to understand the information on the consent. After going through the consent, they will allow time to read the consent form and answer any questions patient may have. The research coordinator/study staff will provide a copy of informed consent to the patient. Once patient signs the consent, the research coordinator/study staff will set him/her up for the carbon monoxide test.

Study staff will approach the patient at a future visit if within the 6-month eligibility timeframe and they have not completed another PRO. Once they complete another PRO, eligibility will be based on their next (most recent) PRO. If the patient returns to clinic within 6 months of the last PRO taken or before taking a new PRO, s/he remains eligible and can consent and complete other enrollment activities. If patient comes back after 6 months then s/he will remain eligible based on their next PRO.

In the CNICS PROs, update the drop down menu item for that participant to note they have “Consented” to the study. If time allows, collect patient’s phone number in order to contact them for follow-up visits and enrolling them in the texting portion of the study on Qualtrics.

Assign the participant a study ID. UW starts at 100; UAB 500; Fenway 1,000.

Carbon Monoxide Test

RA conducts test with participant immediately following consent. If the provider is waiting to see the participant, the CO test can be done after the visit. RA will instruct participant on how to use CO monitor and will step outside of the room while the participant blows into the monitor. Document the results in the tracking log.

Randomization

Randomization will be programmed into the CNICS PRO platform and will occur after the patient consents to the study. The randomization scheme is a 50/50 ratio between the intervention and control arms. Intervention vs. control status will be tracked in the PRO platform.

Intervention Arm:

Provider Confirmation

1. If the patient is in the intervention arm then:
 - a. The patient’s provider will be sent a note in the EMR or give a hard copy note describing which medication the algorithm recommends he/she prescribe the patient.
 - b. RC will send the physician the pharmacotherapy medication sheet (see Appendix) in the EMR for him/her to review the medication option derived from the algorithm, give him/her a hard copy of the pharmacotherapy medication sheet.

Both Arms:

Questionnaire Completion

Give patient additional questionnaires to complete on tablet in separate research room either before or after the visit with provider, depending on the clinic flow that day. If the participant can’t stay to complete the additional questionnaires, you can schedule a time for him to return to complete them, so long as he picks up his prescription at the pharmacy if the provider decides to prescribe him medication. This must be done on the same day as the baseline visit.

Questionnaires:

1. Demographics
2. Smoking Behavior/History
3. Hughes/Hatsukami Withdrawal Scale (HHWS)
4. Fagerstrom Test for Nicotine Addiction (FTND)
5. Questionnaire of Smoking Urges (QSU)
6. Thoughts about Abstinence (TAA)

Texting

Participants will be sent a text-message based survey each week (11 total) between the Initial Visit and the End of Treatment Visit (12 weeks post-Initial Visit). Response options will be listed after every question and participants will respond to the question with the letter or number included in parentheses. The questions below will be administered every week unless otherwise specified.

The Qualtrics platform will be used to send the texts to the participant's cell phone. If the participant doesn't respond one week, call the participant to see if they will complete it over the phone. Otherwise, it will be marked as missing data.

If the participant doesn't have a cell phone that can receive texts, the research coordinator will call the participant weekly to administer the questionnaire over the phone. RAs will call twice over the course of the week (if the participant doesn't answer the first time). After 2 calls, the data will be classified as missing.

- 1. How many cigarettes did you smoke yesterday?**
 - a. Participant responds with number of cigarettes smoked
- 2. Are you taking any medications to help you quit smoking?**
 - a. (Y) Yes
 - b. (N) No
- 3. How good are you at taking your smoking medications as prescribed?**
 - a. (0) Poor
 - b. (1) Fair
 - c. (2) Good
 - d. (3) Very Good
- 4. How confident do you feel that you can quit smoking?**
 - a. (0) Not at all confident
 - b. (1) A little confident
 - c. (2) Both confident and not confident

- d. (3) Somewhat confident
 - e. (4) Very confident
5. **In the last month, how often have you felt nervous or stressed?**
- a. (0) Never
 - b. (1) Almost never
 - c. (3) Sometimes
 - d. (4) Fairly often
 - e. (5) Very often

End of Visit:

1. Give participants \$20 and confirm follow-up appointment time in 12 weeks.
2. Confirm the best number to reach the patient at for the weekly text-it surveys.
3. At the end of the visit, give the patient referral to quit line and a hand out containing smoking cessation tips.

Tracking of Study Participants

Study staff will use the CNICS database to capture baseline, 12 week-end of treatment, 1, 3 and 6 month post-treatment assessments, as well as viral loads, and carbon monoxide measurements. Study staff will use excel logs to capture prescreening, enrollment, randomization, timeline/window of outcome assessments, status of assessments, reminder call status for assessments. All study staff will be trained in Human Subjects Protections, and this data will be handled in accordance with UAB, UW, and Fenway electronic storage and data transfer guidelines.

MEDICATION INFORMATION

If medication is prescribed, the pharmacy will provide a medication fact sheet for the participant and a brief demonstration on how to administer the medication.

Medication List

Name	Method	Dosage	Side Effects
-------------	---------------	---------------	---------------------

Nicotine Patch	Patch	7 mg/14 mg/21 mg	Mild itching, redness, burning, and stinging at the application site may occur. Nausea, dizziness, flushing, heartburn, headache, trouble sleeping, dizziness, anxiety, depression.
Nicotine Gum	Gum	2 mg/4mg	Mouth/Jaw Pain Hiccups Heartburn Nausea Indigestion
Lozenges	Lozenge	2 mg/4 mg	Nausea Mouth/Jaw Pain Hiccups Sore Throat Heartburn Irregular/fast heartbeat
Nicotrol Nasal Spray	Spray	2 mg/4 mg	Nasal Irritation Watery Eyes Runny Eyes Coughing Sneezing
Nicotrol Inhaler	Inhaler	2 mg/4 mg	Coughing Headache Throat Irritation Nausea Jaw/Neck Pain
Bupropion (Wellbutrin/Zyban)	Tablet	150 mg	Anxiety, dry mouth, hyperventilation,

			irregular heartbeats, irritability, restlessness, shaking, trouble sleeping
Varenicline (Chantix)	Tablet	.5 mg/1 mg	Nausea, sleep problems (trouble sleeping or vivid, unusual, or strange dreams), constipation, gas, vomiting

Refills of Medication

UAB: The same refill system used in the clinic will apply- the patient can come pick up their meds without calling or can call ahead of time to ensure the med is ready; this would be the pharmacy number and not the refill number.

Billing for Medication for Study

UAB: The 1917 Pharmacy will bill the study for any medications (copays or full drug cost) that are not covered by the intervention participant's insurance.

Stocking of Meds in 1917 Pharmacy

UAB: The 1917 Pharmacy stocks nicotine patches, lozenges, bupropion and Varenicline. Nicotine gum, nasal spray and inhalers will be ordered as needed.

Follow-up Visits

12 week End of Treatment:

1. If visit is in person, conduct CO test and document results in tracking log.
2. Patient given QQs (FTND, QSU, HHWS, TAA) and QQ on smoking behavior/medication use after patient has seen providers.
3. Give patient \$40 and schedule next study visit.

1 Month Post-Treatment Follow-up:

1. If visit is in person, conduct CO test and document results in tracking log.
2. Patient given QQs (FTND, QSU, HHWS, TAA) and QQ on smoking behavior/medication use. -can be done via text/e-mail if unable to come to clinic. Done after patient has seen providers.
3. Give patient \$40 and schedule next study visit.

3 Month Post-Treatment Follow-up:

1. If visit is in person, conduct CO test and document results in tracking log.
2. Patient given QQs (FTND, QSU, HHWS, TAA, Treatment Satisfaction Survey) and QQ on smoking behavior/medication use. -can be done via text/e-mail if unable to come to clinic. Done after patient has seen providers.
3. Give patient \$40 and schedule next study visit.

6 Month Post-Treatment Follow-up:

1. If visit is in person, conduct CO test and document results in tracking log.
2. Patient given QQs (FTND, QSU, HHWS, TAA) and QQ on smoking behavior/medication use. -can be done via text/e-mail if unable to come to clinic. Done after patient has seen providers.
3. Give patient \$50.

Retention Procedures

Continue to attempt to reach the participant up to six months after the final follow-up visit. After the 6-month mark, the participant can be marked lost to follow-up.

Summary of Compensation

Timepoint	Compensation
Baseline	\$20
12 Week End of Treatment	\$40
1 mo Post-Treatment	\$40
3 mo Post-Treatment	\$40
6 mo Post-Treatment	\$50

Data Collection and Management

All study documentation will be kept in locked file cabinets in study personnel's offices at UAB, UW, and Fenway. The CNICS database can only be accessed by CNICS personnel using UAB, UW, and Fenway computers or encrypted laptops.

Data Analysis

Using Pearson's chi-square test for 2 independent proportions, we will analyze the difference in the proportion of participants with 7-day point-prevalence cessation at 6 months between the treatment arms. Participants for whom we do not have 6-month follow-up data will be assumed to be smoking. We do not anticipate any difference in baseline variables between arms, but if differences do exist, we will utilize a multivariate logistic regression model with cessation as the outcome, treatment group as the primary independent variable, and imbalanced variables which are known to be correlated with cessation as additional independent variables. The same approach will be taken for 24-hour quit attempt – dichotomized yes/no – at 6 months. For cigarette reduction, we will look at the change in number of cigarettes smoked per day at baseline and 6-month follow-up. Either a 2 independent sample *t*-test or the non-parametric Wilcoxon Rank-sum test as appropriate will be used to test for a difference in the change in cigarettes per day between the 2 groups. If necessary, an ordinary least squares regression model with change in cigarettes per day as the outcome adjusting for baseline

In addition to these primary analyses, we will examine outcomes by sex and racial groups to determine moderator effects. For sensitivity analyses, we will exclude participants without 6-month follow-up data. We will also 1) consider count regressions models that can account for time from enrollment until 6 month visit (such as Poisson regression) if actual timing of planned 6-month follow-up visits differs enough between participants; 2) repeat all analyses using end of treatment and 6-month follow-up outcomes; 3) consider employing models that treat site as a clustering variable (such as Cochran-Mantel-Haenszel [41] and Generalized Estimating Equation); and 4) fit longitudinal models with data from all timepoints. These longitudinal models will examine the interaction between treatment group and time. Exploratory analyses will be conducted stratified by site, cigarettes per day at enrollment, and quit goal.

Protection of Human Subjects

Our team has devised a comprehensive plan for ensuring protection of human subjects throughout the course of the proposed study. We will utilize an English-language consent form with common phrasing that describes that no special privileges or considerations will be conferred because of study participation, and that access to medical care will not be affected by the potential participant's decision to enroll in the study. The procedures listed in the following sections detail procedures that have been approved and utilized during recent years of clinical and behavioral trials at each site for collaborative research that utilizes sensitive information from

participants. Our team will make every effort to protect all participants' confidential and private information in order to minimize possible study-associated risks.

All findings related to this research will be available and provided to study participants in accordance with standard practices. Clinical and measurement data used for research studies will be released only in de-identified fashion.

In addition, all study personnel are required to renew Human Subjects trainings annually, or in accordance with their site regulatory mandates.

Study Algorithm

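### Patients can be randomized on a smoking report up to 6 months old although the criterion covers the past month, which allows modest dilution of the primary comparison but not bias between arms

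*Combined protocol and SAP*

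**What the plan says.** Under Eligibility Criteria & Approach, inclusion criterion 3 is "Smoking 5 or more cigarettes per day for the past month". The decision is delegated to the questionnaire platform: "CNICS PRO platform will indicate if the patient is eligible or not for the Algorithm study based on smoking scores".

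Two routes into the study follow.

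- **Same-day route (Screening):** "Patients taking the PRO on the day of the Primary Care Provider (PCP) visit will be screened for the Algorithm study".
- **Earlier-PRO route:** at UAB, under Pre Screening, a biweekly query is used to "identify patients who have previously completed a PRO and qualify based on their smoking score". Under Enrollment, Informed Consent, a patient not enrolled at the PRO visit may be approached later: "If the patient returns to clinic within 6 months of the last PRO taken or before taking a new PRO, s/he remains eligible", and such a patient can then consent and be enrolled.

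The later approach has a limit: "Once they complete another PRO, eligibility will be based on their next (most recent) PRO". A patient who returns after 6 months is also judged on the next PRO. Recruitment Screening and Selection puts PROs some four to six months apart, with a 90-day minimum.

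On allocation, the Randomization section says: "Randomization will be programmed into the CNICS PRO platform and will occur after the patient consents to the study". The Carbon Monoxide Test section places the CO reading after consent, lets it follow the provider visit, and has the result logged. It gives no cut-off. Questionnaire Completion lists a smoking behavior and history form for both arms, to be filled in before or after the provider visit or on a return visit.

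**The concern.** The criterion describes smoking in the month before entry. The enrollment rule accepts a report whose month may have ended about 6 months before randomization. Someone who has since stopped, or dropped below 5 a day, can be randomized by following the plan as written.

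The primary outcome in Data Analysis is 7-day point-prevalence cessation at 6 months. It carries no condition on smoking status at randomization, and no exclusion or adjustment for people abstinent at entry is planned. A person who was abstinent on entry and is still abstinent at 6 months is thus scored as a quit, although no quit took place in the study. Such entrants raise the quit rate in both arms, pull the risk ratio toward 1, cost some power, and feed into the cost-per-quit estimates of Aim 3.

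**Working it through.** **Text check.** I looked for any step between an old PRO and randomization that would confirm current smoking.

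| Step | Could it screen out a non-smoker? |
|---|---|
| The 5-a-day eligibility check under Screening | It belongs to PRO screening; no repeat at a later visit is described |
| Baseline CO test | After consent, possibly after the provider visit; logged, no cut-off |
| Smoking behavior/history form | May follow the visit or be done on a return visit; not an entry condition |
| Randomization | The only stated precondition is consent |

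None does so in the visible text. The exclusion for current cessation treatment has the same gap. The word *or* in the enrollment rule could suggest no time limit, but the same paragraph sends anyone returning after 6 months to the next PRO. The age of the smoking data at consent therefore runs from 0 to about 6 months. One further mismatch: the Approach section has postponers logged for re-approach at their next PRO date, whereas Informed Consent allows an approach before any new PRO.

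**Size.** The documents give no alpha, power, expected quit rates, or share enrolled on an older PRO, so there is no planned figure to reproduce. What follows is illustration.

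Inputs:

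- From the plan: 250 + 200 + 150 = 600, allocated 1:1, so n = 300 per arm.
- Assumed: two-sided alpha 0.05; quit rates among current smokers of 8% (control) and 15% (intervention).
- Assumed: q, the share already abstinent at randomization, 1-3%. For example, 20% on an older PRO with 5% of them stopped gives 0.20 × 0.05 = 1%; 30% with 10% stopped gives 0.30 × 0.10 = 3%.
- Assumed: r, the share of those entrants counted as abstinent at 6 months, either 1 or 0.5, and the same in both arms.

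Formulas:

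- Observed rate in an arm = (1 − q)p + qr.
- Observed difference = (1 − q)(p₂ − p₁), whatever r is.
- Power = Φ[(d − 1.96·SE₀)/SE₁], where SE₀ = √(2p̄(1 − p̄)/n) and SE₁ = √((p₁(1 − p₁) + p₂(1 − p₂))/n).

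With q = 0: d = 0.07, p̄ = 0.115, SE₀ = 0.02605, SE₁ = 0.02589. Power = Φ[(0.07 − 0.05105)/0.02589] = Φ(0.73) = 76.8%.

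| q | r | Control | Intervention | Difference (points) | Risk ratio | Power |
|---|---|---|---|---|---|---|
| 0 | – | 8.0% | 15.0% | 7.0 | 1.88 | 76.8% |
| 1% | 1 | 8.9% | 15.9% | 6.9 | 1.78 | 73.2% |
| 2% | 1 | 9.8% | 16.7% | 6.9 | 1.70 | 69.8% |
| 3% | 1 | 10.8% | 17.6% | 6.8 | 1.63 | 66.6% |
| 1% | 0.5 | 8.4% | 15.4% | 6.9 | 1.82 | 74.7% |
| 2% | 0.5 | 8.8% | 15.7% | 6.9 | 1.78 | 72.7% |
| 3% | 0.5 | 9.3% | 16.1% | 6.8 | 1.73 | 70.7% |

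The loss is about 4 to 10 points of power if every already-abstinent entrant counts as a quit, and about 2 to 6 if half do.

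A second assumed pair, 10% vs 18% with r between 0.8 and 0.5, goes from 80.8% to 76.1-77.5% at q = 2% and to 69.3-72.4% at q = 5%. The direction is the same; the size depends on q.

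**The case against.** The 6-month rule can be read as the shelf life of a screening result in a trial run inside routine clinics. Exposure is limited: the same-day route is unaffected, postponers are to be met at their next PRO, and any newer PRO replaces the old one. The approach script, appendix and study algorithm are not in the available text, and a smoking question could sit in any of them. An already-abstinent entrant becomes a quit only by staying abstinent, providing 6-month data (missing counts as smoking) and being biochemically confirmed as Aim 1 intends, so r = 1 is a worst case. The planned test compares proportions, and their difference barely moves.

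Most of this stands. It limits the size, and it limits the absence claim to what is visible. It does not remove the mismatch: a shelf life of 6 months and a criterion about the past month cannot both describe who may be randomized.

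Three stronger readings are tempting and not supported:

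- **That people who cut down count as quits.** They do not. The outcome is cessation; they breach the criterion only.
- **That one arm is favored, or that type I error rises.** Allocation follows consent, so such entrants balance on average, and with no treatment effect the two arms' expected rates remain equal.
- **That the change in cigarettes per day uses the old PRO value.** The plan does not say which value is the baseline, and both arms complete a smoking form around entry. What can be said is that the source is unstated.

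**Conclusion.** The point holds as a mismatch between the inclusion criterion and the enrollment rule, with no re-check visible before randomization. The consequence is inflated quit rates in both arms and modest dilution. Confidence in the mismatch is high, subject to the sections not shown; confidence in the size is low. The power figures rest on assumed quit rates, alpha, q and r, and on the already-abstinent having the same 6-month abstinence in both arms. If few patients enter on an older PRO, the effect is negligible. It is worth correcting because the remedy is small and the number affected cannot be judged from the plan.

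**What to change.** 1. Reconcile inclusion criterion 3 with the Informed Consent rule. Whenever the PRO is more than 30 days old, re-ask the past-month cigarettes-per-day item at consent, before randomization, and randomize only if the criterion is still met. Confirm at the same time that the patient is not receiving cessation treatment. If the approach script already does this, say so in the protocol.
2. State in Data Analysis that baseline cigarettes per day is the value collected at enrollment, not one carried over from an older PRO.
3. Align the Approach and Informed Consent sections on when a postponing patient may be approached again.
4. For patients already enrolled, report the PRO-to-consent interval by arm and add a sensitivity analysis of the primary outcome restricted to those whose PRO was within 30 days of consent. The interval is fixed before randomization, so the restricted comparison remains a randomized one.

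Cost: a short question at consent and a few lines of text. A few patients will be screened out, and the sensitivity analysis will have fewer patients and so less precision. The 30-day cut-off follows the criterion's own one-month window; a nearby value would serve if fixed in advance.

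### Aim 1's primary outcome is biochemically confirmed abstinence, but the primary analysis sets no CO condition, so unverified or CO-discordant self-reports can count as quits

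*Combined protocol and SAP*

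**What the plan says.** Purpose and Background, Aim 1, hypothesises a "significantly higher proportion of abstinence (biochemically confirmed primary outcome), 24-hour quit attempts" and a greater fall in cigarettes per day, "at 6-months post randomization compared to those in the eTAU group". Abstinence is the primary outcome, and it is to be biochemically confirmed.

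Follow-up Visits gives the same CO instruction at the 12-week visit and at 1, 3 and 6 months post-treatment: "If visit is in person, conduct CO test and document results in tracking log". At the three post-treatment visits the questionnaires, including the one on smoking behaviour, "can be done via text/e-mail if unable to come to clinic". That option is not written for the 12-week visit. No way of verifying a remote report is described.

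Data Analysis compares "the proportion of participants with 7-day point-prevalence cessation at 6 months between the treatment arms" by Pearson's chi-square. Its one rule for missing data is: "Participants for whom we do not have 6-month follow-up data will be assumed to be smoking". The sensitivity analyses exclude those participants and vary the model and timepoint. None concerns verification.

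**The concern.** The outcome declared in Aim 1 and the outcome tested in Data Analysis are tied together by no rule. Someone who answers the 6-month questionnaire by e-mail has 6-month data, so the smoking assumption does not reach them, and nothing else stops a reported quit from being counted. The same holds for someone who attends, reports abstinence and gives a CO reading that contradicts it.

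This matters because no masking of patients, providers or assessors is described. Under Randomization, only the intervention arm's provider is sent the algorithm's recommendation. Under Billing for Medication, at UAB the study covers intervention participants' uninsured medication costs. Over-reporting that differs by arm would enter the result as treatment effect, and equal over-reporting would dilute the risk ratio. The same quit count feeds the incremental cost per quit in Aim 3.

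**Working it through.** **1. Who is classified how, from the text as written**

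| Status at 6 months | Rule in Data Analysis | Can count as a quit? |
|---|---|---|
| No data | Assumed smoking | No |
| In person, reports abstinence, CO agrees | None needed | Yes |
| In person, reports abstinence, CO disagrees | None | Yes |
| Text or e-mail, reports abstinence, no CO | None | Yes |

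The last two rows are not biochemically confirmed. The result does not depend on which 6 months is meant. Six months after randomization falls near the 3-month post-treatment visit (12 weeks of treatment plus 3 months), and that visit and the 6-month post-treatment visit both allow remote completion. This step needs no assumed rate.

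**2. Inputs for an illustration of size**

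From the documents: 600 participants (250 + 200 + 150) allocated 1:1, so 300 per arm. The documents state no alpha, power, quit rate, remote share or over-report rate, so there is no plan figure to reproduce. Everything else here is assumed: two-sided alpha 0.05, true quit rate p, remote share r, and rate f at which remote smokers claim abstinence.

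Apparent quit rate = p + (1 − p) × r × f. The rejection probability uses the normal approximation to the pooled two-proportion test: with difference d, Φ((d − 1.96·SE0)/SE1) + Φ((−d − 1.96·SE0)/SE1), where SE0 is the pooled and SE1 the unpooled standard error.

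**3. Plan as written, no true effect (p = 10% in both arms)**

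| r | f, AT vs eTAU | Apparent rates | Rejection |
|---|---|---|---|
| 40% | 5% vs 5% | 11.8% vs 11.8% | 5.0% |
| 20% | 10% vs 5% | 11.8% vs 10.9% | 6.4% |
| 40% | 10% vs 5% | 13.6% vs 11.8% | 10.1% |
| 40% | 15% vs 5% | 15.4% vs 11.8% | 25.1% |
| 60% | 15% vs 5% | 18.1% vs 12.7% | 44.9% |

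Example: 0.10 + 0.90 × 0.4 × 0.10 = 0.136 and 0.10 + 0.90 × 0.4 × 0.05 = 0.118.

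**4. A true effect of 15% vs 8%, r = 40% in both arms**

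- Every quit verified: 15% vs 8%, risk ratio 1.88, power 76.8%.
- As written, equal 10% over-reporting: 0.15 + 0.85 × 0.4 × 0.10 = 18.4% vs 0.08 + 0.92 × 0.4 × 0.10 = 11.7%, risk ratio 1.58, power 63.5%.
- No CO classed as smoking: 0.15 × 0.6 = 9.0% vs 0.08 × 0.6 = 4.8%, risk ratio 1.88, power 52.8%.

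**5. The corrected rule when remote completion differs by arm**

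With true 10% in both arms and 30% vs 50% remote, the confirmed rates are 0.10 × 0.7 = 7.0% and 0.10 × 0.5 = 5.0%, and the rejection probability is about 18%.

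**The case against.** The strongest defence is that the document should be read as a whole. Aim 1 calls the outcome biochemically confirmed, CO is scheduled at every in-person follow-up, and Tracking of Study Participants says CO readings are captured. Cessation in Data Analysis may be shorthand for the Aim 1 outcome, and 6-month data may be meant to include CO. This stands to the extent that the plan nowhere says unverified reports will count; they can count. It does not close the gap, because no cut-off is given and no rule covers absent or discordant CO. Two analysts could reach different primary results from the same data. One sentence of Data Analysis is cut off in the available text, but it concerns cigarettes per day and is unlikely to hold the missing rule.

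A second objection is that the size rests wholly on assumed rates. That is correct. With equal over-reporting and equal remote completion, type I error stays at 5.0%.

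A third is that the obvious remedy loses more power than the fault it repairs (52.8% against 63.5% in step 4) and can create its own bias (step 5). This stands and shapes the fix.

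A reader might infer two stronger points that the documents do not support:

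- **That participants know their arm.** The recommendation goes to the provider, and the text under Both Arms allows for a prescription in either arm. Open delivery is a fair inference, but how far patients know their allocation is not stated.
- **That the outcome breath test is unwitnessed.** The instruction that staff "will step outside of the room while the participant blows into the monitor" belongs to the test done around consent at baseline. No passage extends it to follow-up.

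**Conclusion.** The concern holds in this form: the rule in Data Analysis yields a different endpoint from the one Aim 1 declares, and unverified or CO-discordant self-reports can count as quits. That follows from the text alone and must be settled before analysis.

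The consequence cannot be sized from the documents. The 6% to 45% false-positive range shows sensitivity under assumed rates and is not an estimate; it requires over-reporting or remote completion to differ by arm. Equal over-reporting leaves type I error alone but, in the assumed 15% vs 8% case, lowers the risk ratio from 1.88 to 1.58 and power from 76.8% to 63.5%. It would be too strong to say that the plan intends to count self-report, or that differential misreporting has been shown.

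**What to change.** In the SAP, before any by-arm analysis:

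1. Define primary abstinence as self-reported 7-day abstinence plus a CO reading below a prespecified cut-off at the primary timepoint.
2. Classify self-reported abstinence with absent or discordant CO as not abstinent.
3. Report self-reported abstinence as a sensitivity analysis.
4. Tabulate remote completion and CO verification by arm.
5. Within existing visits and the contacts already planned under Retention Procedures, seek an in-person CO reading from remote responders who report quitting.

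CO readings are already collected, so items 1 to 4 need only SAP wording, a derived variable and a table. Item 5 takes staff effort. The statistical cost is that true quitters without a CO reading are counted as smoking. This lowers observed quit rates and power, and it can bias the comparison if remote completion differs by arm. The self-report analysis and the verification table must therefore accompany the primary result, and the more readings item 5 obtains, the smaller both problems become.
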